Protocol Title: USING THE FOODIMAGE™ APP TO ASSESS SMART INTERVENTIONS DESIGNED TO IMPROVE NUTRITION & REDUCE FOOD WASTE

PI Name: [name].; [name].; Pennington Biomedical Research Center

Co-Investigators: [name]., PI of the parent award at Ohio State University
[name]., Louisiana State University (LSU)
[name], Ph. D., Pennington Biomedical Research Center

Protocol Version Date: 10/27/2021

IRB Review History

This is a subcontract project with Ohio State University as the lead institution and Pennington Biomedical Research Center (PBRC), part of the Louisiana State University system, as the subcontractor who will conduct the human subjects research. PBRC will pursue the research outlined herein and share the resulting data with [name] at OSU and [name] at LSU.

Objectives

Long-term Goals and Specific Objectives

Our *long-term goal* is to simultaneously improve global sustainability, enhance national food security, and improve U.S. productivity through improved nutritional intake while improving the competitiveness of the U.S. food system by reducing U.S. household food waste. To reduce household food waste and improve individual nutrition, we leverage the FoodImage™ smartphone app ¹, a novel method for measuring household food acquisition, food intake, and food waste decisions, to assess the efficacy of a smart intervention that targets food waste reduction and diet quality improvement. The intervention is designed to improve nutrition by offsetting intake of less nutritious foods with increased fresh fruit and vegetable (FV) intake while simultaneously reducing household food waste via strategies tailored to participating households.

Specific objectives include using the FoodImage app in a randomized controlled trial (RCT), in which we will use the data collected to:

Enroll and Baseline Data Collection	N=46	
Randomly Assign within Matched Pairs	Control (N=23)	Treatment (N=23)
Info on Benefits of FV Consumption	No	Yes
Provision of Free FV Box	Yes	Yes
Intervention	Stress Management	Food Waste Reduction + Replace Less Healthy Foods with FV

We will use the data collected to:

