(1) *Test the effects of free FV provision on:* (a) household food waste levels (mass/grams and energy/kilocalories), (b) total FV acquisition (free FV provision plus purchases post-intervention vs. pre-intervention FV purchases), and (c) the consumption of FV (Food Patterns Equivalents Database, FPED). We hypothesize that free FV provision will increase food waste, total FV acquisition, and diet quality (increase the Healthy Eating Index [HEI]). We will test these hypotheses by comparing baseline and follow-up data from participants randomly assigned to the control condition, which features free FV provision and a placebo (stress management) intervention not focused on food waste. Exploratory analyses will examine the effects on dietary energy intake and if the freely provided FV replace non-FV foods in the baseline diet.

(2) Test if a smart intervention to reduce food waste and replace less healthy foods with FV significantly reduces post-intervention food waste compared to the control group while increasing FV acquisition and consumption compared to pre-intervention baseline. We hypothesize that this smart intervention will increase total FV acquisition and FV consumption compared to baseline, and these increases are not expected to differ significantly from control. It is further hypothesized that those receiving the smart intervention will significantly reduce food waste compared to controls. Exploratory analyses will examine the extent to which the smart intervention had the intended effect of replacing less healthy foods with FV consumption.

Background

The most recent Dietary Guidelines (Dietary Guidelines Advisory Committee 2015; at time of grant submission) ² recommend a dietary pattern featuring greater consumption of FV to reduce the risk of cardiovascular disease, type-2 diabetes, some cancers, and obesity, whose prevention would yield numerous health and economic benefits ³. Despite extensive public messaging and well-documented evidence of health and economic benefits, only about 10% of Americans eat the recommended amounts of FV ⁴ with the high cost of FV identified as one barrier to increasing FV intake ^{5 6}.

Given that FV are the most wasted food category and that FV subsidies have regularly been shown to increase FV expenditures but not consistently been shown to increase FV intake ^{7 8}, additional research is needed to:

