Finally, the FoodImage app, and its data collection methodology, integrates customizable notifications and reminders to remotely prompt participants to record data, resolve data collection problems, etc. These notifications and reminders utilize Ecological Momentary Assessment (EMA) methodology¹¹ to maximize data collection protocol adherence by reminding participants to capture and send food information at relevant times. This notification functionality of FoodImage can also be leveraged to communicate information about ongoing interventions and can facilitate adherence to dietary changes and strategies to reduce food waste.

Increasing household FV consumption while reducing food waste requires behavior to change in two overlapping domains, each of which has been the focus of considerable work^{7 12}. Current efforts to change household level behavior are often compartmentalized, focusing either on increasing FV consumption or reducing food waste, but not on the behaviors together. In doing so, existing interventions fail to consider the linkages between behaviors that occur in households and may affect positive change in one domain with negative or neutral impacts on the other domain (e.g., increase FV consumption but increase food waste or reducing food waste by limiting fresh FV consumption). Hence, it is essential to articulate any unintended consequences that existing programs present across these two domains and create interventions that simultaneously promote behavior change that advance both goals.

Methods

Study Design

We will conduct a randomized controlled trial (RCT) featuring two groups that both receive free boxes of FV. The box of fresh FV will contain about 40% fruit and 60% vegetables and be sufficient to meet 60 ±5% of the household's FV needs as recommended by USDA's MyPlate. The amount of FV provision will scale in proportion to the size of the household as is done with SNAP benefits (as noted earlier, it is estimated that ~20% of participants will actually be eligible for SNAP). The groups differ in the intervention provided, with the treatment group receiving a smart intervention to reduce food waste and replace consumption of less healthy foods with FV and the control group receiving an intensity-matched intervention focused on an unrelated topic (stress management).

Participants

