 - b. FPED values, i.e. serving size, for food intake and consumption of FV including FV inventory, total FV acquisition, and total FV intake
 - c. Quantify baseline diet quality (i.e. food intake as assessed by the HEI)
- 2) Determine how the smart intervention altered:
 - a. Mass (grams), energy (kcal), and macronutrients (g and kcal) for household food waste levels, food purchasing patterns, food intake, and consumption of FV including FV inventory, total FV acquisition, and total FV intake
 - b. FPED values, i.e. serving size, for food intake and consumption of FV including FV inventory, total FV acquisition, and total FV intake
 - c. Quantify diet quality (i.e. food intake as assessed by the HEI)
 - d. Acquisition and intake of non-FV foods
 - e. The percent of household food waste that was FV

Secondary analysis objectives include assessing the demographic (e.g., age, education), household (SNAP eligibility, household size, beginning food inventories), and attitudinal factors (e.g., frugality, health and environmental consciousness) related to the primary analysis targets.

Power analysis

Power analysis was conducted for change in the primary outcome variable (grams [g] of food waste) from baseline to the end of the intervention to detect significant differences between treatment and control groups. Following the methods of our previous study, waste data will be summarized and analyzed by aggregating across measurement days. Based on weekly data from our previous study, the participants in the group receiving a smart food waste reduction intervention reduced their waste at meals by 331 g while the control group only reduced their waste by 33 g (298 g group difference), while the pooled standard deviation of the change in food waste between the control and treatment groups was 295 g, yielding an effect size of 1.01. The power to detect an effect size of 1.01 is 0.92 if there is no attrition (23 per group) and is 0.88 if attrition exceeds the 10% expectation (20 per group or 13% attrition). Given the power analysis is based upon an RCT that did not involve the provision of free FV, we expect effect sizes to be larger in the proposed study due to the presence of free FV, yielding even higher power than projected above.

Provisions to Monitor the Data to Ensure the Safety of Subjects

Adverse events will be monitored at each intervention visit. The PI and his co-investigators will review all data continuously to ensure the safety of each subject.

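### The FV part of Objective 2 judges the smart intervention by the treatment arm's change from baseline, which also contains the effect of the free box

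*Combined protocol and SAP*

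**What the plan says.** Objective 2 uses two comparators. Food waste is to be compared with the control group. The FV outcomes are handled differently: "while increasing FV acquisition and consumption compared to pre-intervention baseline". The next sentence names the cause: "We hypothesize that this smart intervention will increase total FV acquisition and FV consumption compared to baseline". It then adds of the rises that "these increases are not expected to differ significantly from control".

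Both arms receive the box, as the design table under Objectives shows: "Provision of Free FV Box Yes Yes". Under Study Design the box is to be "be sufficient to meet 60 ±5% of the household's FV needs as recommended by USDA's MyPlate". It is first handed out at Visit 2, when the coaching also begins (Procedures). Objective 1 defines total FV acquisition as "free FV provision plus purchases post-intervention vs. pre-intervention FV purchases", so the box is itself part of the outcome.

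Under Theory Driven Hypotheses:
- H1a predicts that FV acquisition, consumption and diet quality rise in the control arm.
- H2a predicts a rise in FV acquisition in the treatment arm and credits the lower effective price and the smart intervention together. It names no comparator.
- H2b predicts higher FV consumption without more energy intake, and better diet quality, with a reference to control that may apply to diet quality only or to both outcomes.

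Item 2 of Study Endpoints opens with "Determine how the smart intervention altered" and lists FV acquisition and intake among the targets, again without a comparator.

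**The concern.** A before-after change in the treatment arm combines the box, the coaching, the passage of time and any effect of repeated recording. The arms are randomised to differ in the content of the intervention (including, in the design table, information on the benefits of FV), not in the box. Only a comparison between arms removes what the arms share.

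The plan's own predictions show the difficulty. H1a says that FV will rise with the box and without the smart intervention. Objective 2 says that the treatment arm's rise should not differ significantly from control. A smart intervention with no effect on FV would produce this same pattern. If the within-arm rise were reported as a result of the smart intervention, the coaching would be credited with what the box did. The plan lists measuring the efficacy of that intervention, and guiding policy on FV provision, among its expected outcomes.

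**Working it through.** **Step 1. Reproduce the plan's power figure, to fix the test conventions.** Inputs from Power analysis: waste reductions of 331 g and 33 g, SD of change 295 g, 23 or 20 per group. Alpha is not stated.

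- Effect size: (331 - 33)/295 = 298/295 = 1.01.
- Two-sample t-test, noncentrality d·√(n/2): 1.01·√11.5 = 3.43 with 44 df, and 1.01·√10 = 3.19 with 38 df.
- Power at two-sided 0.05: 0.918 and 0.875, against 0.92 and 0.88 stated. These agree. One-sided 0.05 gives 0.958 and 0.932, which do not. Two-sided 0.05 is used below.

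**Step 2. What each comparison estimates.** Write the mean change as box + time + smart in the treatment arm and box + time in control, with the box effect taken as equal in both arms.

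- Treatment arm against its baseline: box + time + smart.
- Treatment minus control: (box + time + smart) - (box + time) = smart.

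**Step 3. Behaviour of the within-arm test with smart = 0 and time = 0.** Let d be the box effect in SDs of change. The documents give neither a box effect nor an SD for FV, so d is an assumption shown over a range. The one-sample t-test has n - 1 df and noncentrality d·√n; at d = 0.5 this is 0.5·√23 = 2.40 or 0.5·√20 = 2.24. The last column is the FV pattern that Objective 2 predicts: a significant rise together with no significant difference from control (simulation, 100,000 trials per setting).

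| d (assumed) | Significant rise, n = 23 / n = 20 | Rise and no significant difference, n = 23 / n = 20 |
|---|---|---|
| 0 | 2.5% / 2.5% | 1.7% / 1.7% |
| 0.2 | 14.9% / 13.3% | not run |
| 0.5 | 63.0% / 56.4% | 60.6% / 53.8% |
| 0.8 | 95.6% / 92.4% | 91.6% / 88.7% |
| 1.0 | 99.6% / 98.9% | 94.8% / 94.2% |

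The chance of a significant rise passes 50% at d = 0.43 (n = 23) or 0.46 (n = 20), and 80% at d = 0.61 or 0.66.

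**Step 4. The between-arm test on the same simulated data.** It rejects in 4.9% to 5.1% of trials, and in favour of treatment in about 2.5%, at each box effect simulated (0, 0.5, 0.8 and 1.0 SD).

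**Step 5. Acquisition compared with consumption.** Let B be the box, P0 purchases before and P1 purchases after, over equal periods. The change in acquisition is B + P1 - P0. It is positive unless purchases fall by at least B, and B is 55% to 65% of household need. Consumption has no such identity: the box can be wasted, or can replace FV that would otherwise have been bought and eaten.

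**Step 6. What the between-arm contrast can detect.** With 80% power it detects a difference in change of 0.85 SD (23 per arm) or 0.91 SD (20 per arm).

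**The case against.** The best defence is to read Objective 2 whole. Its FV clause is tied to a food-waste clause that is tested between arms, and the Background gives a reason for the pairing: waste might be cut by limiting fresh FV. On that reading the baseline comparison is a check that FV did not fall. A reader might infer from the table above that a useless intervention would usually meet Objective 2. The documents do not support that. With no effect on waste, the waste test favours treatment about 2.5% of the time (two-sided 0.05 assumed), so both parts together succeed at most that often, whatever the box does. This part of the defence stands.

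A reader might also infer that control plays no part in the FV claim. That too goes too far. Objective 2 foresees the comparison with control and states its expected result, H2a credits the box and the intervention jointly, and H2b can be read as a between-arm test of FV consumption. Endpoint item 2 names no comparator and is compatible with a between-arm analysis. These points narrow the concern but do not remove it. An expected non-significant difference is not a test of an added effect. Without an equivalence margin, and with 0.85-0.91 SD detectable, it would not show that the arms are alike. H2b, if read as a between-arm test of consumption, conflicts with Objective 2.

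Finally, a rise in consumption cannot be called almost guaranteed. The Background itself says that subsidies have not consistently raised FV intake, and with no box effect and no time trend the within-arm test fires at only 2.5%. That limits the size of the problem for consumption. It does not make the comparison one about the smart intervention.

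**Conclusion.** The point holds for the FV component of Objective 2 only. The sentence attributes to the smart intervention a change that estimates box plus coaching plus time. With no smart effect, this test comes out significant upward in about 13-15% of trials at an assumed box effect of 0.2 SD, 56-63% at 0.5 SD and 92-96% at 0.8 SD, against about 2.5% in favour of treatment for the randomised contrast. These figures assume normally distributed changes, two-sided 0.05, no time trend, an equal box effect in both arms and 20-23 participants per arm. The box effect is the assumption that matters most, and the documents do not quantify it. For acquisition a rise is close to built in by the definition of the outcome; for consumption it is uncertain. The food-waste comparison and its power calculation are unaffected.

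**What to change.** 1. In Objective 2 and endpoint item 2, base any statement about the smart intervention's effect on FV acquisition and consumption on the treatment-minus-control difference at follow-up, adjusted for baseline (for example by ANCOVA), with its confidence interval.
2. Keep the treatment arm's change from baseline as a description of free box plus smart intervention, as H2a already words it.
3. Reconcile Objective 2, which expects no FV difference from control, with H2b, and state whether H2b's reference to control covers FV consumption or diet quality alone.
4. Do not read a non-significant difference as similarity to control. If similarity is to be claimed, prespecify an equivalence margin.

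The cost is wording and one analysis of data already collected in both arms. The scientific cost is that the FV conclusion will be less favourable and less precise. The 0.85-0.91 SD detectable with 80% power refers to an unadjusted comparison of change; baseline adjustment may improve on it, by an amount that the documents do not allow one to calculate.

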H1a: FV acquisition, consumption, and diet quality will increase in the control group featuring a reduction in the effective price of fresh FV and

H1b: Food waste will increase in the control group featuring a reduction in the effective price of fresh FV,

where the effective price of fresh FV is reduced via free FV provision (the pick-up site is centrally located with free parking and convenient for most Baton Rouge area residents). According to Hamilton and Richards (Proposition 1) if food waste reduction knowledge (θ) is increased then the amount of fresh food consumed will increase while the amount wasted will decline so long as $F > 1 - \gamma$, i.e., so long as demand for fresh food is not too price elastic. Hence, we forward:

H2a: FV acquisition will increase in the treatment group featuring both a reduction in the effective price of fresh FV and a smart intervention to reduce food waste,

H2b: FV consumption will increase without increasing total energy intake and diet quality will also increase in relation to the control group, and

H2c: Food waste in the treatment group will be less than food waste in the control group.

Expected Outcomes

We expect to assess whether programs that subsidized FV acquisition are efficiently translating program dollars into improved nutrition rather than into increased energy intake and increased FV waste and to develop interventions that ensure funds targeted

to increase household FV acquisition are efficiently translated into improved household nutrition. We will:

1. Assess the impact of free FV provision on FV intake and household food waste production
2. Measure the efficacy of the smart intervention
3. Provide insights to guide future policies and interventions that target increased FV consumption through free or subsidized FV provision.

We also expect to improve upon the efficiency of the FoodImage app through continual assessment of participant feedback and by improving the efficiency of image analysis and data input.

Study Endpoints

Primary analysis objectives follow the hypotheses, which we are sufficiently powered to assess:

- 1) Quantify baseline distributions:
 - a. Mass (g), energy (kcal), and macronutrients (g and kcal) for household food waste levels, food purchasing patterns, food intake, and consumption of FV including beginning FV inventory, total FV acquisition, and total FV intake

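### Objective 2 hypothesizes that FV gains will not differ significantly from control, H2b most naturally predicts more FV consumption than control, and no margin or FV power calculation supports a no-difference claim

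*Combined protocol and SAP*

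**What the plan says.** Objectives, objective (2), makes two statements about FV. The first is against baseline: "We hypothesize that this smart intervention will increase total FV acquisition and FV consumption compared to baseline". The second, in the same sentence, is against control: "these increases are not expected to differ significantly from control". Food waste, by contrast, is expected to be significantly lower than in control.

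Theory Driven Hypotheses restates the treatment-arm predictions. On acquisition: "H2a: FV acquisition will increase in the treatment group featuring both a reduction in the effective price of fresh FV and a smart intervention". This names no control comparator. On consumption and diet quality, H2b reads: "FV consumption will increase without increasing total energy intake and diet quality will also increase in relation to the control group". Both follow from a proposition in the cited household model: "if food waste reduction knowledge (θ) is increased then the amount of fresh food consumed will increase while the amount wasted will decline", subject to a condition on how price-elastic demand is.

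Under Objectives, Study Design and Procedures, both arms receive the free FV box. Only the treatment arm receives information on the benefits of FV, food-waste coaching and coaching to replace less healthy foods with FV.

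Study Endpoints lists FV acquisition, FV intake and the Healthy Eating Index (HEI) under the primary objectives and introduces them with: "Primary analysis objectives follow the hypotheses, which we are sufficiently powered to assess". The Power analysis section covers one endpoint only, the between-group difference in change in grams of food waste.

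**The concern.** Two problems meet here.

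The first is consistency. Objective (2) expects no significant between-arm difference in FV consumption, while H2b, read with its theory, expects a gain over control. Until these are reconciled, a non-significant difference matches one sentence of the plan and a significant gain matches another. The choice between them could then be made after the results are known.

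The second is inference, and it applies to acquisition as well. A prediction of non-significance is part of a stated hypothesis, but failing to reject a null hypothesis is not evidence that it is true. Without a margin, an interval rule or adequate precision, a non-significant result says little about whether the arms are alike. H2b's clause that energy intake will not increase has the same weakness, and its comparator is also unclear.

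The plan aims to learn whether free or subsidized FV turns into better nutrition rather than waste. Whether coaching adds FV intake beyond the box itself is central to that aim.

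**Working it through.** **Inputs.** From Participants and Power analysis: 23 per group enrolled; 20 per group as the attrition case. From Power analysis: waste difference 331 − 33 = 298 g; SD of change 295 g; stated power 0.92 (23 per group) and 0.88 (20 per group). Assumed, because the plan does not give them: two-sided alpha 0.05, an unadjusted two-sample t-test, and FV effects in SD units (no FV SD is stated). True differences of 0.2 to 0.8 SD are an illustrative range.

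**Step 1: reproduce the plan's figure.** Effect size d = 298/295 = 1.01. Power comes from the noncentral t with 2n − 2 degrees of freedom and noncentrality d × √(n/2).
- n = 23: 1.01 × √11.5 = 3.43; power 0.918 (stated 0.92).
- n = 20: 1.01 × √10 = 3.19; power 0.875 (stated 0.88).

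One-sided tests give 0.958 and 0.932, which do not match. The two-sided 0.05 assumption therefore fits the plan's own calculation, and the food-waste figures are sound.

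**Step 2: precision for any between-arm FV difference.** The 95% interval half-width in SD units is t(0.975; 2n − 2) × √(2/n).
- n = 23: 2.015 × 0.295 = 0.59 SD.
- n = 20: 2.024 × 0.316 = 0.64 SD.

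**Step 3: chance of a non-significant result when a difference exists** (1 − power, same method).

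| True difference | 23 per group | 20 per group |
|---|---|---|
| 0.2 SD | 90% | 91% |
| 0.3 SD | 83% | 85% |
| 0.5 SD | 62% | 66% |
| 0.8 SD | 24% | 31% |

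**Step 4: what a no-difference claim would need.** Take two one-sided tests at 0.05 each, true difference zero, normal approximation.
- The margin giving 80% power is (1.645 + 1.282) × √(2/n): 0.86 SD at 23 per group and 0.93 SD at 20.
- At a 0.5 SD margin, power is 4% at 23 per group and about 0% at 20.
- For 80% power at a 0.5 SD margin, n per arm = 2 × (2.927/0.5)², rounded up to 69.

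**Step 5: the alternative of testing superiority.** The smallest difference detectable with 80% power is 0.84 SD at 23 per group and 0.91 SD at 20. The sample is thus imprecise for FV outcomes whichever hypothesis is kept, unless the effect is large.

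**The case against.** The strongest reply concerns grammar. In H2b the reference to the control group can attach to diet quality alone. FV consumption would then be predicted to rise from baseline, as acquisition is in H2a, and Objective (2) would be compatible: both arms eat more FV because both get the box, and treatment improves diet quality by displacing less healthy food. This reading is possible and removes the direct conflict. It is the less natural one. The word also ties diet quality to the consumption claim, and H2b is derived from the effect of waste-reduction knowledge, which only the treatment arm is coached in. Even on the narrow reading, that theory implies a between-arm gain in consumption that Objective (2) does not expect to be significant.

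The conflict also does not extend to acquisition. H2a makes no comparison with control, so only the missing margin applies there.

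A reader might infer that the hypothesis cannot fail. The documents do not support that. Objective (2) fails if FV does not rise from baseline, a result significantly below control fits neither statement, and H2b fails if diet quality does not improve on control. A reader might also infer that the investigators will report non-significance as equality. No section says so; non-difference is worded as an expectation and no decision rule is given. The defensible statement is that nothing in the plan prevents that interpretation.

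Finally, the 0.3 and 0.5 SD effects are assumptions, and the plan specifies no model for the between-arm FV comparison. A covariate-adjusted analysis could be more precise than the figures above.

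**Conclusion.** The point holds for FV consumption as an inconsistency on the more natural reading of H2b. It holds for both acquisition and consumption as a prediction of non-significance without the means to support it. Under a two-sided 0.05 unadjusted t-test, with effects in SD units, a true 0.5 SD difference would be missed in 62% of trials at 23 per group and 66% at 20; a true 0.3 SD difference, in 83% and 85%. The claim in Study Endpoints that the hypotheses are sufficiently powered is supported only for food waste.

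This should be fixed but does not threaten the trial's main comparison. Objective (2) and H2c agree on food waste, and the stated power for it reproduces. The documents do not show which FV hypothesis the sponsor intends, so the passages need reconciling rather than one being presumed correct.

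**What to change.** Before data lock:

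1. Reconcile Objective (2) and H2b into one prespecified FV-consumption hypothesis, with its comparator (baseline or control) named.
2. Delete the prediction of a non-significant difference from control as a hypothesis.
3. Report treatment minus control for FV acquisition, FV consumption (Food Patterns Equivalents Database units) and HEI as estimates with two-sided 95% confidence intervals. State that non-significance will not be interpreted as equality.
4. Name the comparator for H2b's energy-intake clause and report that result as an estimate with its interval. Claim no increase only if a margin has been fixed before data lock and the interval meets it; setting a margin is optional.
5. Limit the statement of sufficient power in Study Endpoints to food waste.

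The cost is protocol wording and a short addition to the analysis section, with no new participants or data. The downside is that some no-difference claims will no longer be available, and the FV intervals may be wide enough to leave the between-arm question open.

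### Objective 2 predicts no significant difference from control in FV consumption, while H2b on its most natural reading predicts a gain over control, and nothing says which governs

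*Combined protocol and SAP*

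**What the plan says.** The Objectives section sets out to "assess the efficacy of a smart intervention that targets food waste reduction and diet quality improvement". Objective (2) then hypothesises that "this smart intervention will increase total FV acquisition and FV consumption compared to baseline", and adds that "these increases are not expected to differ significantly from control".

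Theory Driven Hypotheses cites a proposition that if knowledge of how to reduce waste rises, "then the amount of fresh food consumed will increase while the amount wasted will decline", provided that demand for fresh food is not too price elastic. From this it derives:

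- H2a, on acquisition: "FV acquisition will increase in the treatment group featuring both a reduction in the effective price of fresh FV and a smart intervention". No comparison with control is named.
- H2b: "FV consumption will increase without increasing total energy intake and diet quality will also increase in relation to the control group".
- H2c: waste is lower in treatment than in control.

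Study Design describes "two groups that both receive free boxes of FV". By the design table in Objectives and the Procedures section, only the treatment arm is told the benefits of FV and coached to eat FV in place of less healthy foods.

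Study Endpoints says that the primary objectives follow the hypotheses and that the trial is adequately powered for them. FV intake and the Healthy Eating Index (HEI) are among these objectives. The Power analysis section covers grams of food waste only.

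**The concern.** Objective 2 and H2b appear to make different predictions for the same randomised contrast in FV consumption. The primary objectives rest on the hypotheses, so a reader needs to know which prediction is being tested, and the plan gives no rule.

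The Objective 2 version has a second difficulty. It predicts a non-significant test, with no margin to say how small a difference would count as none. In a small trial such a prediction can be met because the interval is wide, whatever the truth. The stakes are not abstract: the Background gives "reducing food waste by limiting fresh FV consumption" as an example of how an intervention aimed at one behaviour can harm the other. If the treatment arm wasted less partly because it ate less FV than control, a non-significant FV comparison could sit beside a significant waste result and appear to match Objective 2.

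**Working it through.** **1. The statements side by side, by outcome**

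| Outcome | Objective 2, against control | H2a / H2b, against control | Conflict? |
|---|---|---|---|
| FV acquisition | no significant difference | H2a: none stated | No |
| FV consumption | no significant difference | H2b: increase (broad reading) or none stated (narrow reading) | Yes, on the broad reading |
| Diet quality (HEI) | not mentioned | H2b: increase | No |

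The broad reading of H2b is the more natural one. H2b is drawn from the proposition that more knowledge raises fresh food consumed. Both arms receive the box, so the effective price falls in both, and waste-reduction knowledge is what the coaching adds in one arm. The proposition is therefore a between-arm prediction about consumption. The treatment coaching also aims directly at FV intake.

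**2. Checking the method on the plan's own figure**

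Inputs from Power analysis: group difference 298 g, SD of change 295 g, 23 or 20 per arm. Effect size d = 298/295 = 1.01. Two-sample t-test, noncentrality d × √(n/2), n per arm, 2n − 2 degrees of freedom. The documents state no significance level or sidedness; two-sided 5% is assumed.

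- n = 23: noncentrality 1.01 × √11.5 = 3.43, power 0.918 (stated 0.92).
- n = 20: noncentrality 1.01 × √10 = 3.19, power 0.875 (stated 0.88).

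One-sided 5% gives 0.958 and 0.932, which do not match. The two-sided assumption therefore fits the plan's figures. These figures concern waste and say nothing about FV.

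**3. The same test applied to FV consumption**

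The documents give no FV effect or SD, so true differences are assumed, in SD units of the analysed FV outcome. Probability of a non-significant result = 1 − power:

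| True loss against control | 23 per arm | 20 per arm |
|---|---|---|
| 0.3 SD | 0.83 | 0.85 |
| 0.5 SD | 0.62 | 0.66 |
| 0.8 SD | 0.24 | 0.31 |

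The test is symmetric, so the same probabilities apply to a true gain of the same size. The difference detectable with 80% power is 0.84 SD (23 per arm) or 0.91 SD (20 per arm).

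**4. Precision**

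Half-width of the 95% confidence interval = t(0.975, 2n − 2) × √(2/n), in SD units:

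- n = 23: 0.59 SD.
- n = 20: 0.64 SD.

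**5. If no difference is what is meant**

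Two one-sided 5% tests, true difference zero, margins assumed:

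| Margin | Power, 20 to 23 per arm |
|---|---|
| 0.3 SD | 0 |
| 0.5 SD | 0.03 to 0.07 |
| 0.8 SD | 0.60 to 0.70 |
| 1.0 SD | 0.86 to 0.91 |

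For 80% power at a 0.5 SD margin, the normal approximation gives 2 × ((1.645 + 1.282)/0.5)² = 68.5, so about 69 per arm.

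**The case against.** The best defence is grammatical. In H2b the comparison with control can attach to diet quality alone. FV consumption would then be a within-group prediction, as in H1a and H2a, and would agree with Objective 2. This is coherent: HEI is scored across food groups, and the coaching replaces less healthy foods, so HEI could exceed control without more FV being eaten. The cited proposition is also conditional. This stands as a possible reading. It does not remove the problem, because the derivation of H2b and the content of the coaching point the other way and the text does not settle it. On either reading, Objective 2 still predicts a non-significant result without a margin.

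A reader might infer that the nutrition aim cannot fail, because a gain fits H2b and a null result fits Objective 2. The documents do not support that. Objective 2 also requires a rise from baseline, H2b predicts better HEI than control, and a significant FV loss against control would contradict both statements. Nor does the plan say that a non-significant FV result will be reported as confirmation; that would be inference. Study Endpoints also commits to determining how the intervention altered FV intake and HEI, so a loss would not go unexamined.

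A reader might also extend the conflict to FV acquisition. H2a names no comparison with control, and the proposition as cited speaks of food consumed and wasted, so that does not follow.

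**Conclusion.** The point holds for FV consumption. Objective 2 and the most natural reading of H2b disagree on the between-arm contrast, and no rule says which governs. The prediction of no significant difference is not a testable hypothesis with 20 to 23 per arm: a true 0.5 SD loss would be non-significant with probability 0.62 to 0.66. Because Objective 2 also requires a rise from baseline, these probabilities are upper bounds on the chance that such a loss would look as predicted; the joint probability cannot be computed from the documents.

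The figures rest on an assumed two-sided 5% t-test and on assumed FV effects in SD units. The disagreement in wording needs no arithmetic. The primary outcome, grams of food waste, and H2c are unaffected. The change should be made, but it concerns the interpretation of the nutrition results and not the validity of the waste comparison.

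**What to change.** In Objective 2, remove for FV consumption the prediction of no significant difference from control. State the same two-sided between-arm comparison of FV consumption (cup equivalents) and HEI in Objective 2 and in H2b, worded so that the comparison with control clearly covers both outcomes. Report each as an estimate with a 95% confidence interval, and say in advance that a non-significant difference will not be interpreted as evidence of no difference.

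If the investigators do intend no difference, they should instead state an equivalence or non-inferiority margin for FV consumption, justify it, and give its power with 20 to 23 per arm.

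The cost is wording in two places; no new data or visits are needed. The downside is that the FV interval will be wide, about 0.6 SD either side of the estimate, and the report must say so.
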